Patients who signed the informed consent form to participate in an open study IA/PAAG-SI/OA/2020 to evaluate the safety and effectiveness of MD NOLTREXTM, in the case when pain in the target knee joint in the study IA/PAAG-SI/OA/2019 remained the same or increased (on a 100-mm visual analogue scale [VAS]) compared to the rating at Visit 1 of the study IA/PAAG-SI/OA/2019 (or if a decrease in pain severity is less than 40— compared to the rating at Visit 1 of the study IA/PAAG-SI/OA/2019), will receive the injection of MD NOLTREXTM in the target knee (Group A). MD will be administered in accordance with the instructions for use of MD NOLTREXTM: 4.0 ml per injection (2.5 + 1.5 ml, or 2.0 + 2.0 ml from two syringes through one needle [one puncture]) at intervals of one week. The course in an open study is a maximum of 2 injections (the first - at Visit 1, the second - at Visit 2). The number of injections is determined by the doctor depending on the stage of gonarthrosis and the clinical response. In order to avoid overfilling the joint with dense slowly resorbable material, at the good clinical result (reducing the pain severity on a 100 mm VAS by Visit

2 by more than 40— compared to the basal level in the open study[1]), the course of injections will be discontinued.

Patients included in the open part of the study, who have the severity of pain in the target knee joint at the time of inclusion in the open part of the study decreased by 40— or more compared to the assessment on Visit 1 of the IA/PAAG-SI/OA/2019 study, or those who cannot be re-injected with MD NOLTREXTM, a re-injection of MD NOLTREXTM will not be performed on Visits 1 and 2 of the open study (Group B).

A repeated course of MD NOLTREXTM injections in an open study is not possible if any of the following criteria are met:

- 1. Documented intolerance of the studied MD NOLTREXTM;
- 2. Active inflammation in the target knee joint (edema, hyperemia, effusion) at the time of inclusion in the study;
- 3. Inflammatory diseases of the skin and soft tissues in the area of the intended introduction of the studied MD into the target joint;
- 4. History of venous thrombosis and thromboembolism;
- 5. Deviations from the norm in the coagulogram (activated partial thromboplastin time [APTT], prothrombin time [PT], prothrombin index, fibrinogen);
- 6. Hemophilia and other hemorrhagic diatheses, as well as taking anticoagulants and disaggregants;

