- Inflammatory changes in clinical blood analysis (leukocytosis, increased erythrocyte sedimentation rate [ESR]);
- 8. Deviation from the norm (in accordance with the standards of the local laboratory) of the number of platelets;
- 9. Type 1 or type 2 diabetes;
- 10. Acute infectious diseases or infectious exacerbations of chronic diseases (including respiratory tract infections) during the month prior to inclusion in the study.

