#### 3.1.2. Analysis of safety parameters

In this study, the main parameters are safety parameters:

- 1. The frequency of AE and/or SAE;
- 2. Overall assessment of the tolerability of therapy by the investigator and the patient;
- 3. The main parameters of vital activity (heart rate, blood PRESSURE, body temperature, BDD);
- 4. Results of physical examination of the knee joint;
- 5. Results of laboratory and instrumental examination.

In addition, it is planned to evaluate the cumulative (in the framework of a double-blind and open study) frequency of the most likely complications associated with periprocedural or temporary postprocedural (no more than 72 hours) pain or burning.

Other possible side effects and complications of special interest related to the method of intra-articular injection will also be presented separately:

- pain or swelling at the injection site, feeling of bursting, burning, arthralgia, effusion in the joint, synovitis, aseptic acute arthritis;
- infections (pyogenic arthritis, direct infection of the joint at infectious diseases, osteomyelitis, sepsis, etc.);
- subcutaneous neuropathies, drug-induced vascular embolism.

It is planned to analyze the safety parameters for all included patients (safety population or FAS) using descriptive statistics, as well as in the following subgroups:

- those who received only one course of injections in the placebo-controlled study IA/PAAG-SI/OA/2019;
- those who received two courses of therapy both in the placebo-controlled and at Visit 1 (and as per the indications at Visit 2) of the open study;
- those who received two courses of therapy both in the placebo-controlled and at Visit 3 (and as per the indications at Visit 4) of the open study.

For comparison between these subgroups, variance analysis (for quantitative parameters) or the "Chisquare" criterion (for qualitative parameters) will be applied, followed by the application of multiple comparison criteria (if necessary).

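### SAP 3.1.2 compares laboratory results between re-injected and one-course patients without baseline adjustment, although some of those results decide who may be re-injected

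*SAP*

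**What the plan says.** **The test.** SAP 3.1.2 lists "Results of laboratory and instrumental examination" among the five main safety parameters. It describes them for all included patients, then compares three subgroups: one course only, re-injected from Visit 1, and re-injected from Visit 3. The rule reads "For comparison between these subgroups, variance analysis (for quantitative parameters"), with chi-square for qualitative parameters and multiple-comparison procedures if needed. SAP 3.4 sets a two-sided 5% level for all safety parameters. In SAP 3.1.3, ANCOVA with a baseline value is reserved for WOMAC-based measures.

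**Who can be re-injected.** The protocol's study design section states: "A repeated course of MD NOLTREXTM injections in an open study is not possible if any of the following criteria are met". The criteria that bear on laboratory results are:
- "Deviations from the norm in the coagulogram" (criterion 5, either direction);
- "Inflammatory changes in clinical blood analysis (leukocytosis, increased erythrocyte sedimentation rate [ESR"]) (criterion 7, high side only);
- "Deviation from the norm (in accordance with the standards of the local laboratory) of the number of platelets" (criterion 8, either direction);
- "Type 1 or type 2 diabetes" (criterion 9, a diagnosis rather than a glucose limit).

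**Where barred patients go.** They remain in the study. Group B combines pain responders with those barred: "or those who cannot be re-injected with MD NOLTREXTM, a re-injection of MD NOLTREXTM will not be performed on Visits 1 and 2". The same criteria are applied again at Visit 3 before any late course in Group B.

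**The concern.** Some of the outcomes being compared are also the gate into the groups being compared. Among patients whose pain would call for re-injection, those with a raised ESR or leukocyte count at Visit 0 are held back and counted with the one-course patients, unless their results clear by Visit 3. The subgroups then differ on those tests before any injection in this study, and laboratory values persist to some degree within a patient. A difference at Visit 5 can therefore reflect eligibility and not the device.

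Safety of a single or repeated course is the study's stated main purpose. The selection favours the repeated course, so it can create an apparent advantage or conceal a real rise after re-injection.

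**Working it through.** The plan has no figure to reproduce: SAP 3.3 makes no sample-size calculation, and 72 is the size of the earlier study's device arm. The check asks how large a difference selection alone produces.

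**Inputs from the documents:** at most 72 patients; three subgroups; two-sided 5%; the criteria above, applied at Visit 0 and again at Visit 3.

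**Assumptions, not in the documents:** share q outside the limit 2-20%; pain responders at Visit 0 30-70%; correlation between visits r = 0.5-0.8; other bars to re-injection 0-30%; 60% of responders still responding at Visit 3; pain response independent of the marker; no device effect.

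**Step 1. High-side criterion, by hand.** Take a standard normal marker, limit c = z(1-q), half the patients needing re-injection at Visit 0, r = 0.7, and ignore the Visit 3 course and other bars.
- Mean at Visit 0 in re-injected patients: -φ(c)/(1-q).
- Mean in barred patients: φ(c)/q.
- One-course subgroup: responders (share 0.5, mean 0) plus barred patients (share 0.5q), so its mean is 0.5φ(c)/(0.5+0.5q).
- Visit 5 difference: r times the Visit 0 difference.

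For q = 10%: c = 1.282 and φ(c) = 0.1755. Re-injected: -0.1755/0.9 = -0.195. One-course: 0.5×0.1755/0.55 = 0.160. The Visit 0 difference is -0.355 SD, and at Visit 5 it is 0.7×(-0.355) = -0.25 SD. The same steps give -0.07 SD at 2%, -0.14 SD at 5% and -0.41 SD at 20%.

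**Step 2. Simulation with all three subgroups and the Visit 3 course** (1,500 runs per scenario; Visit 5 values; ranges run over the assumptions above).

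| Share above limit | Re-injected minus one-course, SD | ANOVA false positives (nominal 5%) |
|---|---|---|
| 2% | -0.03 to -0.07 | 5-7% |
| 5% | -0.06 to -0.19 | 5-14% |
| 10% | -0.10 to -0.35 | 6-27% |
| 20% | -0.24 to -0.59 | 13-63% |

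A separate simulation at r = 0.7 gives about 7%, 8%, 17% and 42% down the same rows.

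**Step 3. Either-direction criterion (coagulogram, platelets).** With balanced tails the mean difference is 0.00 SD and ANOVA false positives are 4-5%. Out-of-range shares can still separate. With 20% outside and r = 0.8, they are 29% in one-course and 13% in re-injected patients at Visit 5, and chi-square false positives are 28%. With 5% outside and r = 0.5 they are 6% and 5%. Unbalanced tails bring the mean shift back: 8% high and 2% low gives -0.16 SD (r = 0.7).

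**Step 4. No criterion (such as ALT).** The difference is 0.00 SD, with 5% false positives.

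**Step 5. Glucose.** The effect depends on how far diabetic patients' glucose lies above the others'. With 10% diabetic patients, offsets of 0.5, 1, 2, 3 and 5 SD give false-positive rates of 7%, 15%, 36%, 56% and 78%.

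**Step 6. Masking.** Add a true rise of 0.3 SD after re-injection (r = 0.7, high-side limit). The observed difference is +0.04 SD at a 10% share and -0.16 SD at 20%.

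**Step 7. Remedies.** ANCOVA on the Visit 0 value reduces the spurious difference to between 0.00 and -0.10 SD and false positives to 4-9%. Unadjusted change from Visit 0 does not suffice: false positives are 5-32%, because regression to the mean now tends to count against re-injection.

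**The case against.** The strongest reply is that this is a secondary comparison. There is no confirmatory hypothesis, the all-patient safety analysis is descriptive, the protocol and SAP 3.6 say openly that subgroups follow treatment need, and SAP 3.1.1 compares initial characteristics across the same subgroups, so an imbalance could be seen. That moderates the weight of the point. It does not remove it: SAP 3.4 still calls for 5% tests, SAP 3.6 uses the non-random allocation only to decline imputation, and nothing carries a baseline imbalance into the safety comparison.

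A reader might also infer more than the documents support:
- **That raw values are tested.** SAP 3.1.2 is silent on values or changes. The defect is an unspecified variable with no adjustment, and Step 7 shows that an unadjusted change score is not a safe reading either.
- **That normal laboratory results in general are required.** Only the coagulogram, leukocytes/ESR and platelets are gated, with glucose affected indirectly. Liver, renal, uric acid and rheumatoid factor limits are non-inclusion criteria for everyone. No vital sign measurement is a listed bar.
- **That re-injection must look better on every gated test.** Steps 3 and 5 show otherwise for balanced coagulogram and platelet means, and leave glucose uncertain.
- **That the inflation is known to be large.** Entry criteria already exclude systemic inflammatory disease and target-joint inflammation, which may thin the upper ESR and leukocyte tail. The earlier study's entry criteria are not available, so the share barred is unknown.

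**Conclusion.** The concern holds in limited form. As written, SAP 3.1.2 gives a comparison biased in favour of re-injection for mean leukocytes and ESR, probably for mean glucose, and for out-of-range rates of the coagulogram and platelets. The bias is small if 2-5% of patients exceed a high-side limit (at most 0.19 SD, false positives 5-14%). It can be serious at 10-20% (up to 0.59 SD, false positives 6-63%), where it can cancel or reverse a real rise of 0.3 SD.

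The direction follows from the protocol's own criteria. The size rests on assumed shares, correlations and responder rates, and for glucose on an assumed offset. The point should be fixed before analysis, but it does not undermine the all-patient description of safety.

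**What to change.** Only the analysis changes; the re-injection criteria are left as they are. In SAP 3.1.2:
1. State the variable analysed for each laboratory parameter.
2. For parameters tied to a re-injection criterion (leukocytes, ESR, coagulogram, platelets, and glucose through diabetes), replace ANOVA with ANCOVA using the Visit 0 value as covariate.
3. For the subgroup re-injected at Visit 3, use the Visit 3 value as baseline, since it is the last before the decision, or present that subgroup separately against its Visit 3 value.
4. Add normal-to-abnormal shift tables restricted to patients normal at that baseline.
5. Tabulate one-course patients by reason: pain response or barred.
6. Label the subgroup comparison descriptive.

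The cost is SAP wording and a few tables, because the protocol already provides these blood tests at Visits 0, 3 and 5. If only the Visit 0 covariate is used throughout, a small bias remains for the Visit 3 subgroup, with ANCOVA false positives up to about 9% at a 20% share.

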# **3.3.** Planned number of participants in a clinical trial study based on the sample size

This open-label MD NOLTREXTM safety assessment study includes eligible and non-eligible patients who received MD NOLTREXTM as part of the IA/PAAG-SI/OA/2019 study. Therefore, no formal calculation of the sample size was performed. The maximum expected number of study participants is the number of patients who were randomized to the MD NOLTREXTM group in the IA/PAAG-SI/OA/2019 study, i.e. 72 patients.

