## 3.4. Applicable level of significance

Statistical analysis of all the presented efficacy and safety parameters will be carried out at a 5% significance level, using two-way versions of statistical criteria.

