## **3.6.** Procedures to count the missing, non-analyzable, and questionable data

During the monitoring visits to the clinical center, the monitoring specialists authorized by the sponsor will conduct an analysis of patient's eCRF to identify any lack of necessary data. In the absence of data in the eCRF and the availability of relevant information in the primary documentation, the questions to the investigators and instructions for eliminating the inconsistencies will be formulated.

The statistician, authorized by the sponsor, and the principal investigator, when checking the database of research results, will analyze for the presence of dubious, missing and non-analyzable data, and will also formulate questions for investigators.

Researchers, if possible, will eliminate the identified errors in eCRF and inform the main researcher and authorized representatives of the sponsor about this. If the detected errors in the data cannot be eliminated after the completion of patient participation in the study, the statistical analysis of the data will be used to analyze the sensitivity of the resulting parameters to the doubtful data found. Information about the missing, doubtful and non-analyzable data will be presented in the final clinical trial report.

For all parameters of efficacy, safety and tolerability, data recovery is not provided due to the fact that the distribution of patients into subgroups for analysis is based on the actual need for treatment, and is not based on any procedures for distribution into groups, so the missing values cannot be considered as missing accidentally or completely accidentally.

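### SAP 3.1.2 names only the chi-square test for comparing adverse events across three small, need-determined subgroups; p-values from sparse tables can be badly mis-scaled, so exact methods should be named

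*SAP*

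**What the plan says.** SAP 3.1.2 puts safety first: "In this study, the main parameters are safety parameters", with AE and SAE frequency at the head of the list. After a descriptive analysis of all included patients, it compares three subgroups: no repeat course, a repeat course from Visit 1, and a repeat course from Visit 3. Quantitative parameters get analysis of variance. For the rest, the chi-square "criterion (for qualitative parameters) will be applied", with unspecified multiple-comparison procedures to follow if needed.

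SAP 3.4 makes these formal tests: "Statistical analysis of all the presented efficacy and safety parameters will be carried out at a 5% significance level", two-sided. SAP 3.3 sets a ceiling of 72 participants and adds: "Therefore, no formal calculation of the sample size was performed". SAP 3.6 states that "the distribution of patients into subgroups for analysis is based on the actual need for treatment", and the Protocol (Blinding, randomization) agrees, so no subgroup size is fixed by design.

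Neither document names an exact test, an expected-count rule or any other provision for sparse tables.

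**The concern.** The chi-square p-value is a large-sample approximation that is usually trusted when expected counts are about 5 or more. Here at most 72 patients fall into three groups, so the smallest holds at most 72/3 = 24 and may hold far fewer. SAP 2.1 calls for the frequency of each AE, and SAP 3.1.2 lists complications such as sepsis, osteomyelitis and embolism. Tables for events of that kind can be expected to hold very few cases.

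The comparison at stake is one course against two, which is close to the study's stated purpose of assessing safety with single or repeated use. A p-value wrong by one or two orders of magnitude could turn one or two chance events into a reported safety difference. In other tables the same test could miss a difference that an exact test would flag.

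**Working it through.** The documents contain no power, event-rate or subgroup-size figure to reproduce, so this is a calculation under stated assumptions.

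**Inputs.** From the documents: N = 72 at most, three subgroups, two-sided 5%, chi-square with 2 degrees of freedom for event yes/no. Assumed: the splits of 72 shown below, and true event rates of 1% to 10%.

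**Step 1: when are expected counts adequate?** With m patients having the event, a subgroup of size n expects m × n/72 of them. For this to reach 5, m must be at least 5 × 72/n:
- n = 24: 15 events
- n = 12: 30 events
- n = 5: 72 events, that is, every patient

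**Step 2: one event, falling in the smallest subgroup (size n).** Pearson's statistic reduces to X² = N(N − n)/[n(N − 1)]. With 2 degrees of freedom, p = exp(−X²/2), and the 5% critical value is 5.991. The exact Fisher-Freeman-Halton p is n/N. How the other patients split does not matter, provided both other subgroups are larger.
- n = 5: X² = 72 × 67/(5 × 71) = 13.59, p = 0.0011; exact 5/72 = 0.069
- n = 10: X² = 72 × 62/(10 × 71) = 6.29, p = 0.043; exact 10/72 = 0.139
- n = 11: X² = 72 × 61/(11 × 71) = 5.62, p = 0.060; exact 11/72 = 0.153

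So with 72 patients, a single event reaches p < 0.05 by chi-square only if a subgroup has 10 or fewer. The limit is 8 with 60 patients and 7 with 50.

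**Step 3: equal subgroups, three events all in one.** X² = [72²/(3 × 69)] × (9/24 − 9/72) = 6.26, p = 0.044. Exact: 3 × C(24,3)/C(72,3) = 6072/59640 = 0.102.

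**Step 4: error in the other direction.** With 40/26/6 and events 0/2/1, enumeration gives chi-square p = 0.086 and exact p = 0.0496.

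**Step 5: type I error.** I enumerated every table for a given event total (multivariate hypergeometric), then averaged over binomial event totals at rates of 1%, 2%, 3%, 5% and 10%. Entries are chi-square / exact, in percent.

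| Split | 1 event | 2 events | 3 events | Averaged, chi-square | Averaged, exact |
|---|---|---|---|---|---|
| 24/24/24 | 0 / 0 | 0 / 0 | 10.2 / 0 | 0.3 to 4.3 | 0.02 to 2.9 |
| 36/24/12 | 0 / 0 | 2.6 / 2.6 | 6.4 / 3.0 | 0.5 to 4.2 | 0.4 to 4.4 |
| 40/22/10 | 13.9 / 0 | 1.8 / 1.8 | 7.5 / 4.4 | 4.7 to 6.3 | 0.4 to 4.1 |
| 40/26/6 | 8.3 / 0 | 0.6 / 0.6 | 1.7 / 4.96 | 3.1 to 4.9 | 0.2 to 4.3 |
| 34/33/5 | 6.9 / 0 | 13.5 / 0.4 | 1.1 / 1.1 | 4.2 to 6.3 | 0.1 to 4.1 |
| 50/17/5 | 6.9 / 0 | 18.8 / 3.7 | 3.4 / 3.4 | 5.0 to 8.6 | 0.6 to 4.0 |
| 60/7/5 | 16.7 / 0 | 2.6 / 2.6 | 3.5 / 3.5 | 5.7 to 7.1 | 0.5 to 3.5 |

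The two-event figures can be checked by hand. At 34/33/5, chi-square rejects whenever at least one event falls in the subgroup of 5: 1 − C(67,2)/C(72,2) = 345/2556 = 13.5%. At 50/17/5 it also rejects when both fall in the subgroup of 17: (345 + 136)/2556 = 18.8%. At 60/7/5 one event rejects in either small subgroup: 12/72 = 16.7%.

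**The case against.** Much of the case on the other side stands.

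- **The splits are assumed.** The documents give no subgroup sizes, AE counts or event rates. A reader might infer that one event will be declared highly significant, or that the Visit 3 re-injected group will be the smallest. The documents support neither. A single event cannot reach p < 0.05 by chi-square if the smallest subgroup is 11 or more of 72, and sizes depend on treatment need.
- **The decision error is often small.** With one event and 34/33/5, chi-square rejects in 6.9% of cases against a nominal 5%, even though the p-value is badly scaled. In many cells it is conservative. It would be wrong to infer that the test is generally anti-conservative here.
- **The exact test is not free.** With equal subgroups it cannot reject on one, two or three events even if all fall in one subgroup. At 34/33/5 its rejection rate under the null is 0.1% at a 1% event rate. In a safety study this is lost sensitivity.
- **The consequences are bounded.** SAP 3.1 already requires counts, percentages and 95% CIs, so a reader would see 1 of 5. No stopping criterion in SAP 3.5 rests on a subgroup p-value. Whether every AE term is tested, or only overall AE and SAE frequency, is not stated.
- **SAP 3.1 defers the full analysis to a statistical analysis plan.** A fuller text might name an exact test. None is among the documents, and the SAP at hand names only chi-square.

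What does not fall away is the equal-subgroup result. It shows the problem at 24/24/24, without any very small group.

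**Conclusion.** The point holds in a limited form. Chi-square is the only test named for tables in which expected counts will fall below 5 for any uncommon event, and its p-values there can be wrong in either direction. Across the splits checked, type I error given the event total runs from 0% to 18.8%; averaged over event totals at event rates of 1% to 10% it is about 0.3% to 8.6%. The trouble is therefore in reading individual sparse tables, not in a large overall inflation.

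The threshold of 15 events for expected counts of 5 is the most favourable case and follows from N = 72 alone. The p-value pairs and error rates depend on the assumed splits and on enrolment reaching 72.

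**What to change.** In SAP 3.1.2, state that categorical safety tables are compared with the Fisher-Freeman-Halton exact test when any expected count is below 5, and that each subgroup's event proportion is reported with an exact (for example Clopper-Pearson) 95% CI. SAP 3.1 already requires 95% CIs but does not name the method.

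The cost is one or two sentences and a standard software option, with no new data. The statistical price is the conservatism shown above, so the text should add that safety conclusions rest on the proportions and their CIs, and that a non-significant exact test is not evidence of equal safety. For example, 1 of 5 has a Clopper-Pearson interval of 0.5% to 71.6%: the lower limit is 1 − 0.975^(1/5), and the upper limit solves (1 − p)⁵ + 5p(1 − p)⁴ = 0.025. That shows plainly how little one event says.

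The change leaves two problems untouched: the subgroups are formed by treatment need, so differences between them are not causal comparisons, and many AE terms may each be tested at 5%. Both should be stated as limits wherever the subgroup p-values are reported.
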